## VC02-101 Primary Endpoint / Cohort 2:

• Change from baseline to Week 26 in C-peptide area under the curve from 0 to 4 hours (AUC0-4h) following a mixed meal tolerance test (MMTT).

## 2.2.2 Secondary Endpoints

Secondary Safety and Tolerability Endpoints:

#### *VC02-101*:

The comprehensive safety profile of VC-02 combination product implanted for up to two years as measured by:

- All reported AEs
  - The incidence of confirmed immune sensitization defined by presence of donor anti-HLA antibodies absent prior to implant in conjunction with either confirmatory histological observations from at least one explanted unit and/or the presence of clinical symptoms.
- Implant tolerability assessments (e.g., fever, erythema, pain, tenderness, induration) for up to four hours post-implantation and at subsequent visits.
- The incidence of subjects requiring a premature explant due to safety, tolerability, or malfunction issues.

#### VC02-102:

The comprehensive safety profile of VC-02 combination product implanted for up to four months as measured by:

- All reported AEs
- The incidence of subjects requiring a premature explant due to safety, tolerability, or malfunction issues.

#### Secondary Efficacy Endpoints:

#### *VC02-101*:

- Change from baseline to Weeks 8, 12, 16, 20, 26, 39, 52, 65, 78, 91, and 104 in C-peptide area under the curve from 0 to 2 hours (AUC0-2h) or AUC0-4h following an MMTT;
- Time to onset of biological response of C-peptide following MMTT;
- Percent of subjects achieving a positive stimulated C-peptide (defined as >0.2 ng/mL) after implant;
- Change from baseline to Weeks 16, 26, 39, 52, 78, 104 in weekly frequency of hypoglycemic events;
- Percent of subjects free of severe hypoglycemic events between study visits starting with Week 16 (i.e., Weeks 16-20, Weeks 20-26, Week 26-39, Weeks 39-52, Weeks 52-65, Weeks 65-78, Weeks 78-91, Weeks 91-104);
- Percentage of subjects free of severe hypoglycemic events between Week 16 and Week 104 (or early termination).
- Change from baseline to Weeks 16, 26, 39, 52, 78 and 104 in Clarke score;

- Change from baseline to Weeks 16, 26, 39, 52, 78, and 104 in average daily insulin dose;
- Percent of subjects who achieve a 50% reduction in average weekly exogenous insulin requirements from baseline to Weeks 16, 20, 26, 39, 52, 78, and 104;
- Percent of subjects who achieve exogenous insulin independence;
- Percent of time spent with blood glucose values at various cut points (e.g., <54 mg/dL, ≥54 to <70 mg/dL, ≥70 mg/dL to ≤180 mg/dL, >180 mg/dL, and >250 mg/dL) as measured by each subject's continuous glucose monitoring (CGM) device.
- Change from baseline to Weeks 16, 26, 39, 52,78, and 104 in time-in-euglycemic range (≥70 mg/dL to ≤180 mg/dL), time-in-hypoglycemic ranges (<54 mg/dL and ≥54 to <70 mg/dL), and time-in-hyperglycemic ranges (>180 mg/dL and > 250 mg/dL) as measured by each subject's CGM.

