### 2.2.2. Secondary Endpoint Measures

Secondary Safety and Tolerability Endpoints: The comprehensive safety profile of VC-02 combination product implanted for up to two years as measured by:

- All reported AEs
- The incidence of immune sensitization defined by presence of donor anti-HLA antibodies absent prior to implant.
- Implant tolerability assessments (e.g., fever, erythema, pain, tenderness, induration) for up to four hours post-implantation and at subsequent visits.
- The incidence of subjects requiring a premature explant due to safety, tolerability, or malfunction issues.

Secondary Efficacy Endpoints:

- Change from baseline to Weeks 16, 26, 39, 52, 78, and 104 in C-peptide AUC0-2h or AUC0-4h following an MMTT;
- Time to onset of biological response of C-peptide following MMTT;
- Percent of subjects achieving a positive stimulated C-peptide (defined as >0.2 ng/mL) after implant;
- Change from baseline to Weeks 16, 26, 39, 52, 78, 104 in weekly frequency of hypoglycemic events;
- Percent of subjects free of severe hypoglycemic events from Week 16 to Weeks 20, 26, 39, 52, 78, and 104;
- Change from baseline to Weeks 16, 26, 39, 52, 78 and 104 in Clarke score;
- Change from baseline to Weeks 16, 26, 39, 52, 78, and 104 in average daily insulin dose in the seven days preceding the Clinic Visits;
- Percent of subjects who achieve a 50% reduction in average weekly exogenous insulin dose from baseline to Weeks 16, 20, 26, 39, 52, 78, and 104;
- Percent of subjects who achieve exogenous insulin independence; of those subjects achieving insulin independence, the percent achieving HbA1c <7.0%
- Percent of time spent with blood glucose values at various cut points (e.g., <54 mg/dL, ≥54 to <70 mg/dL, ≥70 mg/dL to ≤180 mg/dL, and >180 mg/dL) as measured by each subject's CGM device.

• Change from baseline to Weeks 16, 26, 39, 52, 78, and 104 in time-in-euglycemic range (≥70 mg/dL to ≤180 mg/dL), time-in-hypoglycemic ranges (<54 mg/dL and ≥54 to <70 mg/dL), and time-in-hyperglycemic ranges (>180 mg/dL) as measured by each subject's CGM

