## 10.4.5.1. Secondary Efficacy Analyses

The FAS will be used to analyze the secondary efficacy endpoints, with the analysis for each endpoint performed within each Cohort. Change from baseline in C-peptide  $AUC_{0-4h}$  following an MMTT at Weeks 52 and 104 and change from baseline in C-peptide  $AUC_{0-2h}$  following an MMTT at Weeks 16, 26, 39, 52, 78, and 104 will be analyzed in a similar manner to the ANCOVA performed for change from baseline in C-peptide  $AUC_{0-4h}$  at Week 26, with the relevant baseline as the covariate.

Change from baseline in frequency of hypoglycemic events (24-hour; daytime [start between 6 a.m. - 12 a.m.]; nocturnal [start between 12 a.m. - 6 a.m.]) at Weeks 16, 26, 52, 78; change from baseline to Weeks 16, 26, 52, 78 and 104 in Clarke score; and change from baseline to Weeks 16, 26, 52, 78 and 104 in average daily insulin dose in the seven days preceding the clinic visit will be analyzed using ANCOVA, with treatment group as a factor and the relevant baseline as a covariate.

Time to onset of biological response of C-peptide following MMTT will be assessed using Kaplan-Meier (KM) curves, with the p-value from the logrank test also provided.

The percent of subjects achieving a positive stimulated C-peptide (defined as > 0.2 ng/mL) after implant; the percent of subjects free of severe hypoglycemic events from Week 16 to Weeks 20, 26, 39, 52, 78 and 104; the percent of subjects who achieve a 50% reduction in average weekly exogenous insulin dose from baseline to Weeks 16, 20, 26, 39, 52, 78, and 104; the percent of subjects who achieve exogenous insulin independence; the percent of subjects who achieve exogenous insulin independence and an HbA1c < 7.0% will each be analyzed using Fisher's exact test. The number and percent of subjects in each treatment group and the p-value from the Fisher's test will be provided (at each timepoint, where appropriate).

Percent of time spent with blood glucose values at various cut points at each scheduled visit will be summarized descriptively. The percentages and change from baseline percentages will be

summarized for each cut point (<54 mg/dL,  $\geq$ 54 to <70 mg/dL,  $\geq$ 70 mg/dL to  $\leq$ 180 mg/dL, and >180 mg/dL) and for each treatment group.

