## 6.2 Secondary Efficacy Endpoints and Analyses

Each of the secondary efficacy endpoints will be analyzed using an  $\alpha = 0.05$  level of significance. Given the large number of secondary efficacy endpoints, the p-values for these endpoints will be considered descriptive.

For all secondary efficacy analyses, the FAS (Cohort 2 subjects who meet the FAS criteria) will be used. Change from baseline in C-peptide AUC0-4h following an MMTT at Weeks 52, 78, and 104 and change from baseline in C-peptide AUC0-2h following an MMTT at Weeks 8, 12, 16, 20, 39, 52, 65, 78, 91, and 104 will be analyzed in a similar manner to the ANCOVA performed for change from baseline in C-peptide AUC0-4h at Week 26, with the relevant baseline as the covariate. For subjects who continue to have a C-peptide  $\leq 0.1$  ng/mL as determined by the simplified oral glucose challenge test, the AUC of the respective 2-hour MMTT will be set to 0. A listing of the 2-hr MMTT/C-Peptide and Glucose results will be provided, as well as a listing of the simplified oral glucose challenge.

Time to onset of biological response of C-peptide following MMTT will be assessed using Kaplan-Meier (KM) product-limit method, with the p-value from the logrank test also provided.

The number and percent of subjects achieving a positive stimulated C-peptide (defined as > 0.2 ng/mL) after implant will be analyzed using Fisher's exact test. The number and percent of subjects in each treatment group and the p-value from the Fisher's test will be provided (at each time point, where appropriate).

Change from baseline in frequency of hypoglycemic events (24-hour; daytime [start between 6 a.m. -12 a.m.]; nocturnal [start between 12 a.m. -6 a.m.]) at Weeks 16, 26, 52, 78 will be analyzed using ANCOVA, with treatment group as a factor and the relevant baseline as a covariate. This analysis will be performed using HEs from both the patient-reported diary and from CGM. A listing of hypoglycemic events will be provided for both patient-reported data and from CGM data.

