The number and percent of subjects free of severe hypoglycemic events between study visits (Weeks 16-20, Weeks 20-26, ..., Weeks 91-104, and Weeks 16-104) will each be analyzed using Fisher's exact test. The number and percent of subjects in each treatment group and the p-value from the Fisher's test will be provided (at each time point, where appropriate). These analyses will be performed using both HEs from patient-reported diary and HEs from CGM.

Change from baseline to Weeks 16, 26, 52, 78 and 104 in Clarke score will be analyzed using ANCOVA, with treatment group as a factor and the relevant baseline as a covariate. A listing of the Clarke total score will be provided.

Change from baseline to Weeks 16, 26, 39, 52, 78 and 104 in average daily insulin requirement in the seven days preceding the clinic visit will be analyzed using ANCOVA, with treatment group as a factor and the relevant baseline as a covariate. A listing of insulin dosing will be provided.

The number and percent of subjects who achieve a 50% reduction in average weekly exogenous insulin dose from baseline to Weeks 16, 20, 26, 39, 52, 78, and 104 will each be analyzed using Fisher's exact test. The number and percent of subjects in each treatment group and the p-value from the Fisher's test will be provided (at each time point, where appropriate).

The number and percent of subjects who achieve exogenous insulin independence (both definitions will each be analyzed using Fisher's exact test. The number and percent of subjects in each treatment group and the p-value from the Fisher's test will be provided (at each time point, where appropriate).

Percent of time spent with blood glucose values at various cut points at each scheduled visit will be summarized descriptively. The coefficient of variation (CV) of blood glucose values will be included in the summary. The percentages and change from baseline percentages will be summarized for each cut point (<54 mg/dL,  $\geq$ 54 to <70 mg/dL,  $\geq$ 70 mg/dL to  $\leq$ 180 mg/dL,  $\geq$ 180 mg/dL, and >250 mg/dL) and for each treatment group. The number of subjects with Prolonged HEs (duration > 120 minutes for cut points  $\leq$ 54 mg/dL and  $\leq$ 70 mg/dL) will also be summarized.

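### The SAP drops four of the protocol's six cumulative SHE-free results (Weeks 16-26, 16-39, 16-52 and 16-78) and reports disjoint between-visit intervals instead

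*SAP*

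**What the plan says.** Protocol 2.2.2 lists, among the secondary efficacy endpoints, "Percent of subjects free of severe hypoglycemic events from Week 16 to Weeks 20, 26, 39, 52, 78, and 104". Protocol 10.4.5.1 repeats the definition in the analysis text, "the percent of subjects free of severe hypoglycemic events from Week 16 to Weeks 20, 26, 39, 52, 78 and 104", and assigns Fisher's exact test. There is one fixed start, Week 16, and there are six end points, so the results are cumulative.

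SAP 2.2.2 (secondary efficacy, VC02-101) has two bullets in its place. The first is "Percent of subjects free of severe hypoglycemic events between study visits starting with Week 16", spelled out as "Weeks 16-20, Weeks 20-26, Week 26-39, Weeks 39-52, Weeks 52-65, Weeks 65-78, Weeks 78-91, Weeks 91-104". The second is "Percentage of subjects free of severe hypoglycemic events between Week 16 and Week 104 (or early termination"), a single cumulative span.

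SAP 6.2 follows the SAP's own endpoints: "The number and percent of subjects free of severe hypoglycemic events between study visits", with the list ending "Weeks 91-104, and Weeks 16-104) will each be analyzed using Fisher's exact test". These rows are run on both diary events and CGM-derived events. SAP 6.2 also states that "the p-values for these endpoints will be considered descriptive".

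The SAP revision table records the interval ranges as a sponsor change to be carried into later protocol amendments. Protocol section 10 allows the SAP to modify the protocol, but says that major endpoint changes will be reflected in an amendment.

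**The concern.** The two current documents define different quantities for the same clinical question. The protocol asks what share of subjects has stayed free of SHE since Week 16. An interval row asks what share had no SHE since the previous visit. A subject with an SHE at Week 18 is not free in the Weeks 16-20 row and can be free in all seven rows after it. Under the protocol that subject is not free at any of the six time points.

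What is at stake is the durability result. Four of the six figures the protocol names would not be produced. The retained Weeks 16-104 row is complete only at the end of follow-up. Protocol 10.3.2 and SAP 9.1 plan a review once the last Cohort 2 subject has passed Week 26, and the sponsor may go on from it to an End-of-Phase 2 meeting. For subjects who have reached only Week 26, the SAP then gives Weeks 16-20 and 20-26 but not the protocol's Weeks 16-26. A reader who takes an interval row at a given visit for the protocol endpoint would see too favourable a figure.

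**Working it through.** The documents state no rate, power or expected percentage for this endpoint, so there is no figure of theirs to reproduce.

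**Step 1. Match the spans** (Protocol 2.2.2 and 10.4.5.1 against SAP 2.2.2 and 6.2).

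| Protocol span | Length (weeks) | SAP counterpart |
|---|---|---|
| 16-20 | 4 | identical to the first interval |
| 16-26 | 10 | none (20-26 only) |
| 16-39 | 23 | none (26-39 only) |
| 16-52 | 36 | none (39-52 only) |
| 16-78 | 62 | none (65-78 only) |
| 16-104 | 88 | kept, with early termination added |

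Two of six survive and four have no counterpart. The SAP intervals last 4, 6 and six times 13 weeks (4 + 6 + 78 = 88).

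**Step 2. Direction, without any rate.** A subject free over Weeks 16 to *b* is also free over the last interval ending at *b*. The cumulative-free subjects are a subset of the interval-free subjects. With the same subjects in both, the interval percentage is at least as high as the cumulative one.

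**Step 3. Can the missing figures be recovered from the interval rows?** Suppose each of the four intervals to Week 52 shows 90% free in the same subjects. If the same 10% have events every time, Weeks 16-52 is 90%. If a different 10% do each time, it is 100% − 4 × 10% = 60%. The rows alone cannot tell 60% from 90%.

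**Step 4. Illustrative size.** Assumption: a constant SHE rate *r* per subject-year, with *r* from 0.25 to 2. Then P(free over *L* weeks) = exp(−*r* × *L*/52). For Week 52, the interval has *L* = 13 and the cumulative span has *L* = 36.

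- *r* = 0.25: exp(−0.0625) = 93.9% v exp(−0.173) = 84.1%
- *r* = 2: exp(−0.5) = 60.7% v exp(−1.385) = 25.0%

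Interval v cumulative at each missing time point:

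| Visit | *r* = 0.25 | *r* = 0.5 | *r* = 1 | *r* = 2 |
|---|---|---|---|---|
| Week 26 | 97.2 v 95.3% | 94.4 v 90.8% | 89.1 v 82.5% | 79.4 v 68.1% |
| Week 39 | 93.9 v 89.5% | 88.2 v 80.2% | 77.9 v 64.3% | 60.7 v 41.3% |
| Week 52 | 93.9 v 84.1% | 88.2 v 70.7% | 77.9 v 50.0% | 60.7 v 25.0% |
| Week 78 | 93.9 v 74.2% | 88.2 v 55.1% | 77.9 v 30.4% | 60.7 v 9.2% |

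**Step 5. Between-subject variation.** With gamma-distributed rates of variance parameter *k*, P(free) = (1 + *k* × *r* × *L*/52)^(−1/*k*). For *r* = 0.5 and *k* = 3 at Week 52: 1.375^(−1/3) = 89.9% v 2.038^(−1/3) = 78.9%. The gap falls from 88.2 − 70.7 = 17.5 points to 11.0 points and keeps its sign.

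**Step 6. Interval length.** At a constant 1 SHE per subject-year, the first three SAP rows read 92.6% (4 weeks), 89.1% (6 weeks) and 77.9% (13 weeks), a fall due to window length alone. From Week 26 onward all six rows are 13 weeks.

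**The case against.** The case for the SAP has substance.

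- A reader might infer that the SAP has replaced the cumulative endpoint altogether. It has not. Weeks 16-20 is the same in both documents, and Weeks 16-104 has its own bullet and its own test.
- A reader might infer that the SAP's percentages are inflated. They are not wrong as interval results, and SAP 2.2.2 writes out every interval. They are too high only if read as the protocol endpoint.
- A reader might infer that the rows cannot be compared with one another. Six of the eight are equal at 13 weeks; only the first two are shorter. Fisher's test compares treatment groups within a row, where the nominal interval is the same for all.
- Intervals have a rationale. Protocol section 2 expects maturation over three to six months, and section 1.2 puts maximal effect in nonclinical studies at about nine months. An SHE at Week 18 may precede full function, and later intervals show whether events then stop. The constant-rate illustration does not model that; the subset argument in Step 2 does not depend on it.
- The change is disclosed, p-values are descriptive, no hypotheses are tested, and a listing of hypoglycemic events is planned from which the missing figures could be worked out.

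These points limit the consequence and support keeping the interval rows. They do not supply the four results that the current protocol still lists, and a listing is not a planned analysis. The Weeks 16-104 row is not a full substitute either. The SAP gives no rule for early leavers in that row, so a subject who exits free of SHE at Week 30 would appear to count as free.

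**Conclusion.** The point holds in this limited form: four of the protocol's six cumulative SHE-free percentages are absent from the SAP, and the interval rows cannot restore them. That follows from the two texts and needs no assumption. The direction of the difference also follows by set inclusion, provided that the same subjects enter both figures.

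The size does not follow from the documents, which give no on-study SHE rate. Under assumed constant rates of 0.25 to 2 per subject-year, the Week 52 difference runs from 9.8 points (93.9% v 84.1%) to 35.7 points (60.7% v 25.0%), less with between-subject variation.

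This is a secondary endpoint with descriptive p-values in an open-label, non-randomised study. The primary analysis is not affected. The correction is worth making because it uses data already collected and restores a durability result the protocol states.

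**What to change.** In SAP 2.2.2 and 6.2:

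1. Add the percent free of SHE cumulatively from Week 16 to Weeks 26, 39, 52 and 78, beside the existing interval and Weeks 16-104 rows.
2. Preferably read all six protocol time points (Weeks 20, 26, 39, 52, 78 and 104) from one time-to-first-SHE Kaplan-Meier curve by treatment group. Start it at Week 16 and censor early leavers at exit. This goes beyond the protocol's Fisher's test on percentages, but it handles incomplete follow-up explicitly. It does not remove bias if leaving is related to SHE, which is possible because the risk/benefit assessment in Protocol 10.3.2 considers the frequency of hypoglycemic events. Reasons for exit should be shown with the curve.
3. Keep the interval rows, label them as intervals in every output, and give their lengths (4, 6 and 13 weeks) or report SHE rates per subject-week.
4. Bring the protocol and SAP wording into line through the amendment the SAP already foresees, so that both name the same results.

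The cost is SAP wording, some programming and a few more outputs. No new data are needed. The percentages at later visits will be lower than the interval rows show.

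### The SAP does not compute four of the six cumulative windows in which the protocol measures freedom from severe hypoglycemia (Weeks 16-26, 16-39, 16-52 and 16-78)

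*SAP*

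**What the plan says.** Protocol 2.2.2 lists the secondary endpoint as "Percent of subjects free of severe hypoglycemic events from Week 16 to Weeks 20, 26, 39, 52, 78, and 104". Protocol 10.4.5.1 repeats these windows for analysis by Fisher's exact test: "the percent of subjects free of severe hypoglycemic events from Week 16 to Weeks 20, 26, 39, 52, 78 and 104". All six windows start at Week 16 and differ only in where they end.

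SAP 2.2.2 (secondary efficacy, VC02-101) words the endpoint as "Percent of subjects free of severe hypoglycemic events between study visits starting with Week 16" and lists the intervals "Weeks 16-20, Weeks 20-26, Week 26-39, Weeks 39-52, Weeks 52-65, Weeks 65-78, Weeks 78-91, Weeks 91-104". A separate bullet keeps one cumulative measure: "Percentage of subjects free of severe hypoglycemic events between Week 16 and Week 104 (or early termination" (closing bracket not shown). SAP 6.2 follows the same scheme: "The number and percent of subjects free of severe hypoglycemic events between study visits", in a list that ends "Weeks 91-104, and Weeks 16-104) will each be analyzed using" Fisher's exact test. No other SAP section derives a window from Week 16 to Week 26, 39, 52 or 78.

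The revisions table at the front of the SAP records the between-visit ranges and the Weeks 16-104 measure as sponsor changes to be taken into later protocol amendments. The protocol version that the SAP cites is v8.0 (Amendment #9), and its text still has the cumulative windows. Section 10 of the protocol lets the SAP depart from the protocol, but requires major changes to endpoints or their analyses to appear in an amendment. On inference for secondary endpoints, SAP 6.2 says "the p-values for these endpoints will be considered descriptive".

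**The concern.** The two documents ask different questions under nearly the same endpoint name. The protocol asks what share of subjects has had no SHE since Week 16. The SAP intervals ask what share has had none since the previous visit, so a subject who had an event in one interval can be counted as free in the next.

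With descriptive p-values, the reported percentage is the result, so a change in what it measures matters even though no test is at risk. Timing matters too. Protocol 10.3 and SAP 8 allow a descriptive report once all subjects reach Week 26, and Protocol 10.3.2 and SAP 9.1 describe a review after Week 26 that can lead to an End-of-Phase-2 meeting. For that date the SAP yields Weeks 16-20 and 20-26 but not the protocol's 16-26, and the Weeks 16-104 row cannot yet be complete. The documents do not say whether SHE-freedom would be among the key endpoints in that report.

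There is also a question about early leavers. Protocol 10.3.2 plans a risk/benefit assessment at 9 to 12 months that can end participation. Because the Weeks 16-104 measure allows early termination as its end, a subject who leaves event-free at Week 40 could be counted as free after 40 − 16 = 24 weeks rather than 104 − 16 = 88. The SAP does not say how such a subject is counted.

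**Working it through.** Neither document states a rate, sample size or power for this endpoint, so there is no planned figure to reproduce. The check compares the windows, traces one subject, and then illustrates the size.

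**1. Windows side by side**

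| Window (weeks) | Protocol 2.2.2, 10.4.5.1 | SAP 2.2.2, 6.2 |
|---|---|---|
| 16-20 | yes | yes |
| 16-26 | yes | no |
| 16-39 | yes | no |
| 16-52 | yes | no |
| 16-78 | yes | no |
| 16-104 | yes | yes |
| 20-26, 26-39, 39-52, 52-65, 65-78, 78-91, 91-104 | no | yes |

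The protocol has 6 windows and the SAP has 8 + 1 = 9. Two are in both, so 6 − 2 = 4 are in the protocol only and 9 − 2 = 7 in the SAP only.

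**2. One subject.** Take one SHE at Week 18 and none later. Under the protocol the subject is not free in 6 of 6 windows. Under the SAP the subject is not free in Weeks 16-20 or in Weeks 16-104, and is free in 7 of the 8 intervals.

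**3. Direction.** A subject free from Week 16 to a given visit is also free in the interval that ends at that visit, because the interval lies inside the window. In the same subjects, the interval percentage is therefore never below the cumulative one.

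**4. Can the missing figures be recovered?** Suppose 90% are free in each of k intervals. If different subjects have the events each time, the cumulative figure is 100 − 10k. If the same subjects have them every time, it is 90%.

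| Window | k | Possible cumulative figure |
|---|---|---|
| 16-26 | 2 | 80% to 90% |
| 16-39 | 3 | 70% to 90% |
| 16-52 | 4 | 60% to 90% |
| 16-78 | 6 | 40% to 90% |

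The interval percentages do not determine the cumulative one.

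**5. Size, under assumed rates.** With a constant rate r per subject-year, the SHE-free proportion over w weeks is exp(−r × w/52). Example at r = 0.5 and Week 52: the interval is exp(−0.5 × 13/52) = 0.882, and the cumulative figure is exp(−0.5 × 36/52) = 0.707. Entries are interval / cumulative, in percent.

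| Assumed r | Week 26 | Week 39 | Week 52 | Week 78 | 16-104 (in both) |
|---|---|---|---|---|---|
| 0.1 | 98.9 / 98.1 | 97.5 / 95.7 | 97.5 / 93.3 | 97.5 / 88.8 | 84.4 |
| 0.25 | 97.2 / 95.3 | 93.9 / 89.5 | 93.9 / 84.1 | 93.9 / 74.2 | 65.5 |
| 0.5 | 94.4 / 90.8 | 88.2 / 80.2 | 88.2 / 70.7 | 88.2 / 55.1 | 42.9 |
| 1 | 89.1 / 82.5 | 77.9 / 64.3 | 77.9 / 50.0 | 77.9 / 30.4 | 18.4 |

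**The case against.** The case for the SAP is substantial. It keeps the longest and least favourable cumulative window. It discloses the change. Each interval row is labelled with both of its ends, so nobody is told that Weeks 39-52 means free up to Week 52. From Week 26 on, the six intervals are all 13 weeks long, which suits a product expected to mature over three to six months. Hypoglycemic events are listed, so no data are lost. All of this stands.

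It does not supply the four missing results. The Weeks 16-104 row helps to bracket them, but only loosely. At 1 per year, the interval rows put Weeks 16-52 between 100 − (7.4 + 10.9 + 22.1 + 22.1) = 37.5% and 77.9%. For Weeks 16-78 the interval event percentages sum to more than 100 (7.4 + 10.9 + 4 × 22.1 = 106.7), so only the 16-104 row gives a floor: 18.4% to 77.9%.

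A reader might infer four stronger points that the documents do not support:

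- *That a subject with an SHE counts as free from then on.* This is true only of the interval rows, and only without a further SHE. The Weeks 16-104 row still counts the subject as not free.
- *That unequal interval lengths are a fault of the SAP, creating a false decline.* The protocol windows are 4, 10, 23, 36, 62 and 88 weeks long, all unequal. At a constant 1 per year they fall through 92.6, 82.5, 64.3, 50.0, 30.4 and 18.4%. The SAP intervals give 92.6, 89.1, then 77.9% throughout. Length dependence is no argument for the cumulative windows.
- *That this is an undisclosed change or a programming slip.* The revisions table shows a deliberate sponsor decision.
- *That 1 SHE per year is the expected rate.* Inclusion criterion 11 can be met by a CGM value below 54 mg/dL with no SHE, whereas Protocol 7.10.4 reserves SHE for events needing another person's help.

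**Conclusion.** The mismatch holds on the current text of both documents: four protocol-specified secondary results have no derivation in the SAP and cannot be reconstructed from what it reports. The effect is on interpretation. The interval figures answer a different question and, in the same subjects, can only be equal to or more favourable than the cumulative figure at the same visit.

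The size depends on a rate that the documents do not give. At Week 52 the gap runs from 97.5 − 93.3 = 4.2 percentage points at 0.1 per year to 77.9 − 50.0 = 27.9 points at 1 per year. It assumes a constant rate, independent events and no dropout.

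Whether the change is major in the sense of Protocol Section 10 is a judgement. Either way, the protocol version that the SAP cites does not yet carry it. The trial states no hypotheses, so nothing here touches type I error or power.

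**What to change.** In SAP 2.2.2 and 6.2, add Weeks 16-26, 16-39, 16-52 and 16-78 beside 16-20 and 16-104, and report these six as the protocol-defined endpoint. State how a subject who leaves before a window ends is counted, including in the Weeks 16-104 row. Keep the between-visit intervals as a supplementary display of change over time. If the sponsor prefers the interval definition as the endpoint, the protocol should be amended to say so.

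The cost is four more rows, from event data already collected, plus a sentence on early leavers. The percentages at Weeks 26 to 78 will look less favourable than the interval figures.
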